The study will employ a randomized, allocation-concealed, multicenter, placebo-controlled, multi-period crossover design (Schmid et al, 2018). This multi-period crossover randomized, controlled trial allows comparability and assessment of efficacy through repeated exposures within each subject to the active treatment and a control (placebo) in randomized sequence. Such multi-period crossover designs are ideal for treatments with rapid onset of action and short half-life such as the asset under study here. We have strived to minimize the complexity of this powerful design by using only 2 blocks with 2 periods each. The modest additional complexity of the proposed multi-period crossover design, compared to a parallel-groups design, is justified by the marked improvement in efficiency. The gains in efficiency afforded by the multi-period crossover design allow a substantial reduction in sample size without sacrificing statistical power. For example, our simulation experiments (with sample sizes ranging from 30 to 50, carryover effects ranging from 0 to 0.2, and an effect size of 0.4) indicated that the parallel design yields statistical power ranging from 0.20-0.25, whereas our proposed 2-block multi-period crossover design yields power ranging from 0.9-1.0.

The trial will compare an active treatment vs. placebo. The study will employ a multi-period crossover design with two blocks. Each block will consist of two treatment periods with each period lasting 6 weeks. Treatment assignments (active drug versus placebo) will be randomized for each patient to the two periods within each block. The period length of 6 weeks was chosen based on several considerations: (i) Most efficacious analgesic drugs demonstrate separation from placebo by 6 weeks; (ii) The decision to move CNTX-6970 forward to Phase 3 will require a clinically meaningful separation from placebo by 6 weeks; and (iii) In this Phase 2 study, implementing a treatment block longer than 6 weeks would make the overall design more challenging and burdensome by extending the duration of overall testing beyond 6 months.

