## 5.3 Randomization and Blinding

For entry into the study and randomization, all eligibility criteria MUST be met (i.e., all inclusion criteria and no exclusion criteria specified in the protocol). Patients who meet inclusion/exclusion criteria at the Baseline Visit (day 0) will be randomized. After documentation of written informed consent and the screening period, clinical sites will confirm eligibility and complete randomization by accessing the Almac's centralized web-based system for randomization and drug management - the Interactive Web Response System (IXRS). Subjects will be randomized equally between treatment sequences shown in Figure 1: Drug:Placebo:Placebo:Drug or Placebo:Drug:Drug:Placebo. A standard block randomization will be used, stratifying by K-L grade (stratum 1 K-L grade 1 or 2, and stratum 2 K-L grade 3 or 4) to achieve balance on randomization sequences. The randomization will be implemented by the IXRS vendor in consultation with the study statisticians. After Randomization, drug will be dispensed.

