## 6 Sample Size

The sample size for this study was determined based on the primary efficacy aim to detect clinically meaningful and realistic effects of CNTX-6970 (300 mg BID) compared to placebo in the multi-period crossover

design model. Power was computed for effect sizes ranging from 0.25 to 0.50 using Monte Carlo simulation. Data were simulated from multi-period crossover models with block, period, and carryover effects, and varying within and between subject variability.

Although carryover effects can be efficiently isolated and estimated in the analysis stage by using the mixed-effects models proposed in Section 7, power for the primary hypothesis was computed using only WOMAC-A assessed during the last 2 of 6 weeks per treatment period to minimize carryover effects. The power of the test depends on the relationship of the between-subject variability to the within-subject variability. In general, the between-subject variability is larger than the within-subject variability, but a range of Between/Within (B/W) variance ratios (5/1, 2/1) were investigated. With a sample size of  $n = 55$  per arm, using a two-sided Type I error rate of  $\alpha = 0.05$ , the power to detect an effect size (for the active treatment vs. placebo) of Cohen's  $d = 0.35$  exceeds 95% when the ratio  $B/W = 2/1$ .

Assuming a 15% early termination (e.g., dropout) rate during each of the 4 periods will yield a sample size of approximately  $n = 29$  with complete observations at all treatment periods. If we conservatively assume that only subjects with complete data will be analyzed, the corresponding power with  $n = 29$  exceeds 80% when the ratio  $B/W = 2/1$  with an effect size as low as 0.30. Figure 2 shows the results of a simulation study to evaluate the power of this design. Because we will use all available data from all enrolled subjects in the analysis, the actual power in the case of 15% early termination per treatment period will be larger than what Figure 2 shows. If the ratio B/W is larger than 2, say B/W=3, 4 or 5, the power for detecting the treatment effects is much larger. For example, with only 29 participants, if B/W=5, the power to detect an effect of magnitude Cohen's  $d = 0.35$  exceeds 0.95. Note that the reported test-retest reliability of the WOMAC-A measure is 0.86, which corresponds to a  $B/W = 7$ .

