## 7 General Analysis Considerations

All demographic and baseline variables will be summarized by means, standard deviations, medians, and interquartile ranges (IQR) for continuous measures. Frequency and percentages will be reported for all categorical measures (including binary measures).

The general approach for statistical inference for aims associated with outcomes measured at multiple periods will utilize a mixed-effects multi-period crossover model with 2 blocks and 2 treatment periods per block (of length 6 weeks). Maximum likelihood estimation will be used primarily for parameter estimation and likelihood ratio tests will be used to test hypotheses under the primary and secondary objectives. Significance of an active treatment effect versus placebo will be determined by testing if the treatment effect coefficient differs from zero in the mixed-effect model. When there is a possibility of carryover effects, the multi-crossover model will incorporate carryover effect terms. Only carryover effects from active to placebo will be formally modelled. For outcomes recorded only at baseline and week 24, an appropriate generalized linear model will be used to estimate and test for the active treatment effect, controlling for covariates noted below and also the baseline value of the outcome.

All hypothesis tests will be two-sided using  $\alpha = 0.05$  significance level, and  $p$ -values unadjusted for multiple testing will be reported. The justification for this decision is that this is Phase II investigation and all assessed outcomes are of specific and unique interest. Much more important than testing hypotheses is the efficient estimation of all quantities of interest, and this will be carried out throughout the analyses. Treatment effect point estimates with 95% confidence intervals will be reported along with estimates of other model parameters, regardless of whether the null hypotheses were rejected or not.

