### 9.2 Secondary Efficacy Analyses

The outcomes for Aims 3, 4 and 5 in Section 4 are assessed at multiple time points throughout the study.

**Aim 3.** Outcome (a) WOMAC-C is assessed at baseline and each study visit through week 24. Outcome (b) HADS (anxiety and depression scales which will be modeled separately) is assessed at in-person visits except baseline. Outcome (c) PGIC is assessed at week 3 and week 24 only. Outcome (d) PROMIS Sleep Disturbance Scale – 6A is assessed at baseline and at in-person visits through week 24. Outcome (e) Sleep Duration Question is assessed at baseline and week 24 only. Outcome (f) Daily NRS is collected daily for the week prior to each study visit and these daily NRS values will be modeled in the analysis. The analysis plan for outcomes (a), (b), and (d), and (f) will be similar to the analysis for aim 2 except that the model will adjust for possible carryover effects in placebo-treated periods that are preceded periods with the active drug treatment. To incorporate the modeling of carryover effects, we will use a modification of model (1):

$$y_{i(s)jkm} = \beta_0 + \gamma_j + \delta_k + \beta_1 X_{i(s)jk} + \lambda_{drg} Z_{i(s)jk,drg} + \beta'_2 \mathbf{w}_{i(s)} + b_s + b_{i(s)} + \epsilon_{i(s)m}, \quad (2)$$

where  $\lambda_{drg}$  is used to model carryover effects with  $Z_{i(s)jk,drg} = 1$  if the treatment at block  $j$ , period  $k - 1$  is drug for patient  $i(s)$  in site  $s$ ; all other terms in the model are defined as in (1). Hypothesis 4 for these measures correspond to  $H_0 : \beta_1 = 0$  versus  $H_a : \beta_1 \neq 0$  from model (2).

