### 9.3 Exploratory Analyses

**Aim 6.** If CNTX-6970 is more effective than placebo, we will evaluate the following characteristics of its effect: (a) onset of action; (b) carryover effect after treatment discontinuation. We will study the change of symptoms over time using a time trend in our statistical models within each of the 6-week treatment periods to model the weekly WOMAC-A measure. Under this aim, the interest is not in hypothesis testing, but

rather in understanding the progression and magnitude of onset of action and the carryover effects of the CNTX-6970 compound. This approach will allow an elucidation of the nature of action of the compound. Specifically, we will study the change of symptoms over time using the following mixed-effect multi-period crossover model that incorporates a time trend within each of the 6-week treatment periods to model the weekly WOMAC-A measure:

$$y_{i(s)jkm} = \beta_0 + \gamma_j + \delta_k + \beta_1 X_{i(s)jk} + \alpha_0 t_{i(s)jk} + \alpha_1 X_{i(s)jkt_{ijkm}} + \lambda_{0.drg} Z_{i(s)jk,drg} + \lambda_{1.drg} Z_{i(s)jk,drg} t_{i(s)jk} + \beta'_2 \mathbf{w}_{i(s)} + b_s + b_{i(s)m} + \epsilon_{i(s)m}, \quad (3)$$

where  $t_{i(s)jkm}$  is the patient's  $i(s)$  time measure (at site  $s$ ) within block  $j$  and period  $k$  at the  $m$ th assessment and the common notations are defined as in equation (1). The coefficient  $\alpha_0$  is the slope for change of symptoms during a placebo treatment period, when that period was preceded by none or a placebo treatment period;  $\alpha_1$  (the slope of the change of symptoms during an active treatment period) is a measure of the speed of the onset of action of the active drug; counting week 6 of the previous period as the baseline for the next period,  $\lambda_{0.drg}$  is the active treatment's carryover effect at the start of a placebo treatment period that follows an active treatment period;  $\lambda_{1.drg}$  is the difference in the slopes of treatment change during placebo treatment between two conditions: when the placebo treatment period is preceded by active treatment versus when the placebo treatment period is preceded by no or placebo treatment. Thus  $\lambda_{1.drg}$  will measure the speed of carryover effect disappearance after the active treatment is discontinued.

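### Aim 6, model (3): the drug period that follows drug is fitted as a fresh onset, so a gradual effect gives too small an onset slope α1, too large a β1 and an overstated carryover λ0

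*SAP*

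**What the plan says.** SAP section 5.3 randomizes equally to two sequences, "Drug:Placebo:Placebo:Drug or Placebo:Drug:Drug:Placebo". Period 3 of the second sequence is therefore drug directly after six weeks of drug.

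SAP section 9.3 (Aim 6) models weekly WOMAC-A with a time variable t that restarts in each 6-week period, "counting week 6 of the previous period as the baseline for the next period". Every active period has level shift β1 and slope α0 + α1. The SAP says that α1 "is a measure of the speed of the onset of action of the active drug". Placebo periods are split by history: λ0 is the carryover at the start of a placebo period after drug, and λ1 compares placebo slopes "when the placebo treatment period is preceded by active treatment versus when the placebo treatment period is preceded by no or placebo treatment". Active periods are not split.

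SAP section 7 confirms the asymmetry: "Only carryover effects from active to placebo will be formally modelled". Section 9.2 describes the carryover term in the same way ("the model will adjust for possible carryover effects in placebo-treated periods that are preceded periods with the active drug treatment") and defines Z by the treatment in the preceding period of the same block, which leaves it undefined for the first period of block 2.

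Aim 6 is conditional on efficacy. The SAP says that it is about describing onset and carryover, not testing.

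**The concern.** An onset slope can be seen only in a period that starts off drug. The drug-after-drug period starts with the effect already present, and by the SAP's own convention its baseline is an on-drug value. Model (3) still forces it to share β1 and α1 with the three active periods that do start off drug.

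If the effect builds up over weeks, α1 then averages onset slopes with a continuation slope, and β1 (the effect at t = 0) takes up part of the established drug level. Because block, period and carryover terms are fitted jointly, λ0 moves as well. Both Aim 6 questions, onset and carryover, would be described wrongly. More patients do not help, because the error lies in the model's mean structure.

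**Working it through.** **Inputs from the documents.** Two sequences 1:1 (SAP 5.3); four 6-week periods with weekly WOMAC-A (SAP 5.1, 9.3); 15% dropout per period and between/within variance ratios (B/W) of 2, 5 and 7 (SAP 6); random subject intercept and AR(1) errors (SAP 9.1).

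**Assumed, because the documents do not give them.** The AR(1) coefficient φ (0 to 0.85) and the true onset curve. Covariates and site are left out.

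**Plan's own figure.** None bears on model (3). As a check on the dropout input, 55 × 0.85⁴ = 28.7, which is the SAP's 29 completers.

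**Method.** Take noise-free weekly means (t = 1 to 6) for both sequences and project them by generalized least squares on the fixed effects of model (3), with Z = 1 only in placebo periods that follow drug. Pain reduction is positive and the full effect is 1.

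**Base case.** Linear onset over 6 weeks, flat placebo, no true carryover, flat drug-after-drug period. Truth: α1 = 1/6 per week, β1 = 0, λ0 = 0.

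With independent errors the result can be checked by hand:

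- Slope: α1 is the plain average of the four active slopes, (1/6 + 1/6 + 0 + 1/6)/4 = 0.125, which is 0.125/0.1667 = 0.75 of truth.
- With 15% dropout per period, weight each active period by the fraction remaining. Periods 1, 2, 3 and 4 have 0.850, 0.7225, 0.6141 and 0.5220, and the drug-after-drug period is period 3. The ratio is (0.850 + 0.7225 + 0.5220)/2.7086 = 0.773.
- Level at mean t = 3.5: an active period that starts off drug has 3.5/6 = 0.583; the drug-after-drug period has 1, an excess of 0.417. The fitted active level is 0.354 + 3.5 × 0.125 = 0.792, so half the excess (0.208) goes into the active level. Hence β1 = 0.792 − 0.4375 = 0.354. The same 0.208 appears in λ0 as false carryover.
- Fitted week-1 effect: 0.354 + 0.125 = 0.48, against a true 1/6 = 0.17. Half the full effect is reached at (0.5 − 0.354)/0.125 = 1.2 weeks, against 3.

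Complete data, B/W = 2 (α1 and β1 hardly change at 5 or 7):

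| φ | α1 / truth | β1 (truth 0) | excess in λ0 |
|---|---|---|---|
| 0 | 0.750 | 0.354 | 0.21 |
| 0.3 | 0.668 | 0.397 | 0.27 |
| 0.5 | 0.603 | 0.435 | 0.33 |
| 0.7 | 0.584 | 0.461 | 0.41 |
| 0.85 | 0.659 | 0.459 | 0.52 |

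The lowest α1 ratio is 0.580, near φ = 0.65. With dropout, α1 is 23% too small at φ = 0 and 30-37% under AR(1). Adding an indicator for active-after-active and its product with t returns α1/truth = 1.000, β1 = 0 and λ0 = 0 in every setting.

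**Other onset shapes** (complete data, φ = 0, flat drug-after-drug). α1 is again 0.75 of its repaired value, but β1 as written v repaired is:

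- linear over 2 weeks: 0.77 v 0.67
- exponential, half-time 1 week: 0.67 v 0.52
- exponential, half-time 2 weeks: 0.46 v 0.25

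**Continued improvement.** If the drug-after-drug slope is a quarter, half or all of the onset slope, α1 is 19%, 12.5% or 0% too small with independent errors, and 27-35%, 21-28% or 8-15% for φ 0.5-0.85. With an exponential curve of half-time 2 weeks that keeps rising through the second drug period, the ratio to the repaired value is 0.79 at φ = 0.

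**Immediate onset.** With the full effect at the first weekly record, α1 = 0 and β1 = 1 with or without the added terms.

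**Price of the repair.** Var(α1) rises 1.11-fold (φ = 0) to about 1.26-fold; Var(β1) rises 1.3- to 1.9-fold. Break-even effect for the RMSE of α1: d = √(Var repaired − Var as written) / (bias per unit d), with d on the total SD and W the variance of one weekly record (assumed). At n = 55 with dropout and B/W = 2:

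- 6-week linear onset: 0.20-0.24 SD
- half-time 1 week, or linear over 2 weeks: about 0.3-0.5 SD
- half-time 0.5 week: higher still

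**The case against.** The strongest reply is that the base case suits the drug badly. Protocol D.1 calls the design ideal for drugs with rapid onset and short half-life, such as this one. Protocol K.2 gives a mean half-life of 15.8 to 16.6 hours and an estimated pharmacodynamic duration of 8 to 12 hours. The sentence "Most efficacious analgesic drugs demonstrate separation from placebo by 6 weeks" is an upper limit for analgesics in general, not evidence of a 6-week ramp. All this stands, and it makes the point conditional. It does not dispose of it: receptor pharmacodynamics are not pain onset, and Aim 6 exists because onset is not known. A model that is unbiased only when onset is immediate is a weak tool for measuring it.

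A second reply is that Z might look back across blocks. If it did, and wear-off mirrored onset, there would be no bias. But the text ties Z to placebo periods after drug, and with no carryover that reading still leaves α1 at 0.61-0.64 of truth.

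A reader might infer that the whole false immediate effect comes from the drug-after-drug period and that the two terms remove it. That holds only for a near-linear onset over most of the period. With curved or shorter onsets much of it comes from fitting a straight line and survives the repair. A reader might also infer that the repair lowers error throughout the planning range of SAP section 6 ("Power was computed for effect sizes ranging from 0.25 to 0.50 using Monte Carlo simulation"). At B/W = 2 that holds for the 6-week linear onset but not for the faster ones, where the break-even lies inside or above that range.

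**Conclusion.** The point holds in conditional form and is minor. As written, model (3) misstates onset speed and carryover whenever the effect builds up over weeks. On the assumed 6-week linear onset with complete data, α1 is 25% too small with independent errors and 33-42% under AR(1), β1 is 35-46% of the full effect instead of 0, and λ0 is too large by about 0.2-0.5 of the full effect. For the other onset shapes with a flat drug-after-drug period, α1 is 25% or more below its repaired value.

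These sizes rest on an assumed φ, an assumed curve and a flat placebo course. They shrink if improvement continues in the second drug period and vanish if onset is complete by the first weekly record. Nothing in the documents shows which case applies.

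The consequence stays within an exploratory aim without tests. A reader might infer that the efficacy conclusions are at risk. They are not at risk from this point: the primary analysis uses model (1) on the last two weeks of each period, and Aims 3 to 5 do not use model (3).

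**What to change.** Before unblinding, in SAP section 9.3:

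1. Add to model (3) an indicator for an active period preceded by an active period, and its product with t. Then α1 and β1 come from the three active periods that start off drug, and λ0 is no longer distorted.
2. State that Z = 0 in block 2, period 1 when the treatment is drug.
3. Describe α1 as the active slope minus α0, which is what the equation gives.

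This changes SAP wording and code only, not the conduct of the trial. The statistical cost is Var(α1) up about 1.1- to 1.26-fold and Var(β1) of model (3) up 1.3- to 1.9-fold. If onset turns out to be fast or the effect small (below the break-even values above), the added terms lose some precision in α1 for little or no gain. Even after the change β1 should not be read as an immediate effect, because a straight line fitted to a curved onset still leaves one.

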WOMAC Part A (WOMAC-A) assessed only in the last two weeks of each 6-weeks treatment period will be used for this primary analysis in order to avoid any carryover effects, which are expected to vanish after 4 weeks; the specific carryover effect of the two doses of CNTX-6970 will be studied under Aim 3.

HYPOTHESIS 1: CNTX-6970 300mg BID is superior to placebo with respect to symptoms measured by WOMAC Part A.

The hypothesis testing is based on the WOMAC-A assessed only in the last 2 weeks of each 6-week treatment period. This provides a more than adequate 4-week washout interval. The adequacy of this 4-week period is based on extensive pharmacokinetics (PK) and pharmacodynamics (PD) of the study agent. The PK/PD analyses were performed for single dose and multiple ascending dose (MAD) studies using both QD and BID dosing regimens. For the single dose study, the PK study showed that the mean half-life ranged from 15.8 to 16.6 hours. For PD, the CNTX dossier reports that "... based on the half-life of CNTX-6970 determined in humans it is estimated that the duration of the PD may be between 8-12 hours." Specifically, after two doses of 300mg the plasma level is 10ng/ml 36 hours after dosing. The PD effect is less than 50% at 10ng/ml based on the MCP-1 interaction with CCR2. Hence, we anticipate a more than adequate washout period. Additionally, under Aim 6 (see below), we explicitly study the potential carryover effects in the statistical modeling. The statistical models will utilize a standard approach to adjust for carryover effects in a multi-period crossover design when estimating treatment effects, and allows for testing for the existence of carryover effect (Chen and Chen, 2014).

Aim 3: Assess the efficacy of CNTX-6970 (300mg BID) in comparison to placebo with respect to secondary outcome measures related to OA of the knee: (a) WOMAC-C (function subscale), (b) Hospital Anxiety and Depression Scale (HADS), (c) Patient Global Impression of Change (PGIC), (d) PROMIS Sleep Disturbance Scale – 6A, (e) Sleep Duration Question, and (f) Daily Knee Pain Intensity on a 0-10 NRS.

HYPOTHESIS 2: CNTX-6970 300mg BID is superior to placebo with respect to symptoms measured by (a) WOMAC-C (function subscale), (b) Hospital Anxiety and Depression Scale (HADS), (c) Patient Global Impression of Change (PGIC), (d) PROMIS Sleep Disturbance Scale– 6A, (e) Sleep Duration Question, and (f) Daily Knee Pain Intensity on a 0-10 NRS.

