#### 4.4.2 Primary Efficacy Endpoint

The primary efficacy endpoint is pain in the index knee, measured weekly using the WOMAC-A (Pain subscale) (Bellamy *et al.*, 1988). The index knee will be determined using the averaged screening period WOMAC-A scores by knee – the knee with the greater score at the end of screening is defined as the index knee going forward. Subjects must complete 4 WOMAC-A's at minimum during the screening period to determine the index knee. We will use the numerical rating scale (NRS) version of the WOMAC-A with the subject assessing each of 5 questions using an 11-point (0 to 10) scale; the total score is the sum of the individual item scores (range 0-50). A higher WOMAC score represents worse symptom severity. All WOMAC subscales show strong evidence of validity and reliability (Salaffi *et al.*, 2003), and are the most frequently used primary endpoints for OA trials because of their strong assay sensitivity (Jung *et al.*, 2018). Assessments during the last 2 weeks of each treatment period will be used to test the primary hypotheses in order to avoid possible carryover effects of unknown duration. All weekly measurements of WOMAC-A will be used to study the course of OA pain symptoms during treatment, including onset of action and carryover effects.

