## 5 Study Methods

### 5.1 General Study Design and Plan

This is a multi-crossover design with 2 blocks and 2 periods per block. Each period lasts 6 weeks. Patients will be randomized to one of the treatment sequences shown in Figure 1. The Schedule of Events Table in

the Protocol gives the timing of the outcome assessments. In general, we will be analyzing the data on an intent-to-treat basis (ITT).

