### 9.1 Primary Efficacy Analysis

For the efficacy Aim 2, data from the WOMAC Part A (WOMAC-A) assessed only in the last two weeks of each 6-weeks treatment period will be used for this primary analysis in order to avoid any carryover effects, which are expected to vanish after 4 weeks. Hypothesis 1 in Section 4 will be tested using the following random-effects multi-period crossover model that employs block and period effects to compare the active treatment to placebo (Zucker *et al.*, 1997; Chen and Chen, 2014). Specifically, the model is:

$$y_{i(s)jkm} = \beta_0 + \gamma_j + \delta_k + \beta_1 X_{i(s)jk} + \beta_2' \mathbf{w}_{i(s)} + b_s + b_{i(s)} + \epsilon_{i(s)m}, \quad (1)$$

where  $i(s)$  is the index for patient  $i$  at site  $s$ ;  $\beta_0$  is the intercept;  $j$  is the index for block,  $j = 1, 2$  and  $\gamma_j$  is the block effect;  $k$  is the index for period,  $k = 1, 2$ , and  $\delta_k$  is the period effect;  $m$  is the measurement time;  $y_{i(s)jkm}$  is the primary outcome for subject  $i(s)$ , block  $j$ , period  $k$ , time  $m$ ;  $\beta_1$  represents the treatment effect, and  $X_{i(s)jk}$  is an indicator for active treatment ( $X_{i(s)jk} = 1$ ) or placebo ( $X_{i(s)jk} = 0$ ) for patient  $i(s)$ , in block  $j$ , during period  $k$ ;  $\mathbf{w}_{i(s)}$  is a vector of baseline characteristics (e.g., age, sex, K-L grade indicator) for patient  $i(s)$  and  $\beta_2$  is a vector of coefficients for those baseline characteristics;  $b_s \sim N(0, \sigma_{site}^2)$  is a random site effect and  $b_{i(s)} \sim N(0, \sigma_b^2)$  is a subject-level random effect (nested within site);  $\epsilon_{i(s),m}$  is a random error with an  $AR(1)$  structure:  $\epsilon_{i(s),m} = \phi \epsilon_{i(s),m-1} + u_{i(s)m}$ , with  $u_{i(s)m} \sim N(0, \sigma_u^2)$ . The subject-level random effects will model the repeated measures within subjects. The block and period effect terms will accommodate changes in mean pain scores across blocks and periods of the design.

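### SAP 9.3, Aim 6: if the on-drug week-6 score is the t = 0 response of the next placebo period, λ0 and λ1 measure the loss of effect on stopping, not carryover

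*SAP*

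**What the plan says.** SAP 5.3 randomizes to "Drug:Placebo:Placebo:Drug or Placebo:Drug:Drug:Placebo", and SAP 5.1 states "Each period lasts 6 weeks". The periods run back to back with no separate washout. For Aim 6, SAP 4.4.2 says "All weekly measurements of WOMAC-A will be used to study the course of OA pain symptoms during treatment".

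Model (3) in SAP 9.3 has block and period effects, treatment X, a linear time term t within each period, X×t, a carryover indicator Z and Z×t. Z is 1 for placebo that follows drug within a block. The text interpreting the coefficients says that, "counting week 6 of the previous period as the baseline for the next period", λ0 "is the active treatment's carryover effect at the start of a placebo treatment period that follows an active treatment period". It adds that λ1 "will measure the speed of carryover effect disappearance after the active treatment is discontinued".

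Protocol F.1.8 lists WOMAC-A among the Week 6 visit measures and has the next kit dispensed at that same visit. The week-6 score therefore reflects the outgoing treatment. Protocol K.3 describes Aim 6 without the baseline rule.

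**The concern.** In a placebo period after drug, a t = 0 response taken from the previous week 6 is an on-drug score labelled X = 0, Z = 1. The X terms vanish there, so λ0 has to absorb the drug effect, and λ1 draws a straight line from that point towards the later placebo scores. Both are then non-zero whenever the drug works, whether or not anything persists after stopping. Aim 6 is run only if the drug is more effective than placebo, so the artefact would be present whenever the analysis is done.

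Model (3) is the only model in the SAP with carryover terms for WOMAC-A; model (2) is for secondary outcomes. SAP 9.1 limits the primary analysis to the last two weeks of each period "in order to avoid any carryover effects, which are expected to vanish after 4 weeks", and Protocol K.2 mentions the Aim 6 modelling as an additional study of carryover. A spurious curve fading over four to five weeks could be misread beside that statement. The onset estimates of Aim 6(a) come from the same fit.

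**Working it through.** **Plan's own figure.** None is given for λ0 or λ1, so there is nothing to reproduce.

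**Inputs from the documents.** The two sequences and 6-week periods (SAP 5.1, 5.3); weekly WOMAC-A (SAP 4.4.2); the terms of model (3), with a random subject intercept and AR(1) errors (SAP 9.1, 9.3).

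**Assumptions.** Drug changes the score by E from week 1 on drug and by exactly 0 from week 1 on placebo, so true carryover is zero. Such a rapid offset is plausible: Protocol K.2 says "the mean half-life ranged from 15.8 to 16.6 hours", and 168/16.6 = 10.1 half-lives fit in one week. AR(1) φ is not given; 0, 0.3 and 0.6 were used. Between/within variance ratios of 2 and 7 gave the same coefficients. Site and baseline covariates were omitted because they do not affect within-subject contrasts.

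**Step 1, by hand.** Fit a line to one post-drug placebo period: y = E at t = 0, and y = 0 at t = 1 to 6. Mean t = 3, Σ(t − 3)² = 28 and Σ(t − 3)y = −3E.
- Slope = −3E/28 = −0.107E per week.
- Intercept = E/7 + 3 × 3E/28 = 13E/28 = 0.464E.
- The line reaches zero at 13/3 = 4.3 weeks.

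**Step 2, full model (3).** Expected generalized least squares coefficients over both sequences, with the week-6 score kept as t = 6 and also entered as the next t = 0, and the Week 0 score as t = 0 of the first period:

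| φ | λ0 | λ1 per week | zero at −λ0/λ1 | β1 | α1 per week |
|---|---|---|---|---|---|
| 0 | 0.54E | −0.107E | 5.0 weeks | 0.69E | 0.080E |
| 0.3 | 0.74E | −0.165E | 4.5 weeks | 0.70E | 0.049E |
| 0.6 | 1.04E | −0.222E | 4.7 weeks | 0.68E | 0.022E |

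The true values are λ0 = λ1 = α1 = 0 and β1 = E. If the score is moved to t = 0 rather than used twice, λ0 is 0.59E to 1.05E, with zero at 4.2 to 4.8 weeks.

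**Step 3, same model on t = 1 to 6 only.** λ0 = λ1 = α1 = 0 and β1 = E for every φ.

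**Step 4, gradual onset.** Onset with a 1-week time constant, or linear over 4 weeks, continuing through back-to-back drug periods; offset still immediate.
- With t = 0 rows: λ0 is 0.58E to 1.11E, with zero at 4.5 to 6.0 weeks.
- Weeks 1 to 6 only: λ0 is 0.05E to 0.34E. In the worst case λ1 is −0.034E, so the excess at week 1 is 0.34E − 0.034E = 0.31E.

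This remainder has a different source. Z = 1 occurs only in the second period of a block, and placebo with Z = 0 only in the first. Carryover and period effects are therefore separated only through the drug periods, and model (3) gives a drug-after-drug period the same onset line as a fresh start.

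**Step 5, fitted carryover in the primary window (Step 2 coefficients).**
- Week 5: φ = 0, 0.536E − 5 × 0.107E = 0.00E; φ = 0.3, 0.743E − 5 × 0.165E = −0.08E; φ = 0.6, 1.044E − 5 × 0.222E = −0.07E.
- Week 6: −0.11E, −0.25E and −0.29E, opposite in sign to a lasting benefit.

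**Step 6, visibility in one trial.** Simulation with known variances, 400 trials per setting, instant on/off drug, d = 0.35, φ of 0 or 0.3, ratio 2. The 95% interval for λ0 excluded zero in 60–70% of trials with n = 55, and in 35–43% with n = 29 (55 × 0.85⁴ = 28.7). With weeks 1 to 6 only, it did so in about 3–7% across the settings run, against a nominal 5%.

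**The case against.** The strongest reply is that the clause is not a data-set definition. It stands in a sentence interpreting coefficients and can be read as fixing only the time origin, with t = 0 the moment of the switch. The rest of SAP 9.3 leans that way: time is defined within block and period, and under SAP 9.1 X is the treatment in that block and period, so an on-drug week-6 score belongs to the earlier period with X = 1. Nothing in the SAP says that scores enter twice. This stands: the bias depends on how the clause is read, and the double entry in Step 2 is one way to carry the clause out, not something the SAP states. But the clause speaks of week 6 as the baseline, which most naturally means using that score. Two analysts could follow the same text and get λ0 near zero or near E.

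It is also fair that the zero-crossing is a derived ratio that the SAP does not promise to report, and that a starting point near the on-drug effect could describe an offset curve. The SAP, however, names these coefficients carryover and the speed of its disappearance, and that meaning fails here.

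Finally, Aim 6 is exploratory, conditional on efficacy and not aimed at testing. That limits the stakes, but Protocol K.1 promises point estimates and 95% intervals for all estimated effects, so the numbers would be reported.

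**Conclusion.** The point holds on the natural reading of the clause. λ0 and λ1 would then measure the drop on stopping drug. With zero true carryover and an instant on/off effect, λ0 is about 0.5E to 1.0E, the line reaches zero at about 4.5 to 5 weeks, β1 is about 0.7E, and a false α1 of 0.02E to 0.08E per week appears. These figures rest on assumed φ and onset shape. On the time-origin reading the bias is zero for an instant drug.

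A reader might infer that the primary result or its weeks 5–6 window is compromised. The documents do not support that. Model (1) has no carryover term and uses only the last two weeks; SAP 9.1 rests washout adequacy on PK/PD data; Protocol K.2 brings in Aim 6 only as a supplement; and Step 5 shows no lasting benefit in that window. A reader might also infer that restricting the fit to weeks 1 to 6 removes all bias. It does so for an instant drug; gradual onset leaves about 0.05E to 0.3E. What is affected is the interpretation of the exploratory onset and carryover estimates.

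**What to change.** In SAP 9.3, before unblinding:

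- Delete the clause on week 6 as the next period's baseline, or state that it sets only the time origin and that no t = 0 response row is entered.
- Fit model (3) to weeks 1 to 6 of each period, so that each WOMAC-A score is used once, under the treatment being taken when it was recorded.
- Define λ0 as the excess at week 1 after the switch, for example by coding time as t − 1 in the Z terms, and λ1 as its change per week from there.
- State that gradual onset can still leave a smaller apparent carryover, so a modest λ0 should not be read as residual drug effect on its own. Z-by-week indicators are an optional check on the straight-line decline; they add parameters.

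The cost is a short SAP edit and a few lines of code, with no new data. Week 0 and previous week-6 scores stop being outcome rows in the next period; the Week 0 score can still serve as a covariate.
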